8.9 Study Termination

The study may be stopped at his/her study site at any time by the site investigator. Allergan may stop the study (and/or the study site) for any reason with appropriate notification.

9. Adverse Events

Adverse events occurring during the study will be recorded on an adverse event case report form. If adverse events occur, the first concern will be the safety of the study participants.

9.1 Definitions

9.1.1 Adverse Event

An adverse event is any untoward medical occurrence in a patient or clinical investigation patient administered a pharmaceutical product and that does not necessarily have a causal relationship with this treatment. An adverse event can therefore be any unfavorable and unintended sign (including an abnormal laboratory finding), symptom, or disease temporally associated with the use of a medicinal (investigational) product, whether or not related to the

medicinal (investigational) product. In addition, during the screening period, adverse events will be assessed regardless of the administration of a pharmaceutical product.

Note: Adverse events must be collected once informed consent has been obtained, regardless of whether or not the patient has been administered study drug.

Progression of treatment indication including new or worsening of anticipated clinical signs or symptoms, which are collected as clinical efficacy variables and assessed as unequivocally associated with the disease progression and /or lack of efficacy, should NOT be reported as adverse events unless the disease progression is greater than anticipated in the natural course of the disease.

Adverse events will be assessed, documented, and recorded in the CRF throughout the study (ie, after informed consent has been obtained). At each visit, the investigator will begin by querying for adverse events by asking each patient a general, non-directed question such as "How have you been feeling since the last visit?" Directed questioning and examination will then be done as appropriate. All reported adverse events will be documented on the appropriate case report form.

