6.3 Safety Measures

- adverse events
- BCVA (LogMAR)
- biomicroscopy
- ophthalmoscopy
- intraocular pressure (IOP)
- urine pregnancy test (female patients only)
- PSA (male patients only)
- hematology, serum chemistry, and urinalysis
- vital signs
- male scalp hair evaluation assessed by the investigator using the Norwood Male Pattern Baldness grading scale
- female hair evaluation (upper lip, chin, cheeks, and scalp) assessed by the investigator using the Ferriman and Gallwey scoring (0 to 4) scale for facial hair and the Female Androgenetic Alopecia Ludwig grading scale for the scalp

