7.2.2 Secondary Efficacy Variables

There are total 8 secondary efficacy variables evaluated at month 6 as listed below.

- ***Change from Baseline in TBUT***

The change from baseline in TBUT will be analyzed as the first secondary efficacy variable. For TBUT, the mean of 3 measurements will be computed at each visit for each eye. The mean value of the study eye will be used for the analysis.

- ***Complete Blurred Vision Response***

Similar to overall ocular discomfort, blurred vision will be assessed by each patient based on a 0 to 4 scale. Proportion of patients with complete blurred vision response defined as a blurred vision score of 0 will be analyzed as a secondary efficacy variable.

- ***Complete Corneal Sodium Fluorescein Staining Response***

The complete corneal sodium fluorescein staining response is defined as a secondary efficacy variable. A responder is defined as a patient with a corneal sodium fluorescein staining score of 0 based on the Oxford scheme.

- ***Complete Ocular Burning Response***

Similar to overall ocular discomfort and blurred vision, a 0 to 4 scale will be used to assess the burning symptom experienced by patients. Proportion of patients with complete ocular burning response defined as a burning score of 0 will be analyzed as a secondary efficacy variable.

- ***Change from Baseline in Overall Ocular Discomfort Score***

In addition to the responder analysis, the change from baseline in overall ocular discomfort score will be computed and analyzed as a secondary efficacy variable.

- **≥ 1 Grade Improvement from Baseline in Overall Ocular Discomfort Score**

The proportion of patients who achieved ≥ 1 grade improvement in overall ocular discomfort score from baseline (ie, change from baseline in raw score ≤ -1) will be analyzed as a secondary efficacy variable.

- **≥ 2 Grade Improvement from Baseline in Overall Ocular Discomfort Score**

[figure not shown]
The proportion of patients who achieved ≥ 2 grade improvement from baseline (ie, change from baseline in raw overall ocular discomfort score ≤ -2) will be analyzed as a secondary efficacy variable.

[figure not shown]
- **$\geq 50\%$ Improvement from Baseline in Overall Ocular Discomfort Score**

The percent change in overall ocular discomfort score (OODS) defined as below will be computed for each patient:

$$[(OODS \text{ at month 6} - OODS \text{ at baseline})/OODS \text{ at baseline}] \times 100$$

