7.3 Hypothesis and Methods of Analysis

In general, continuous data will be summarized with descriptive statistics (number of patients, mean, standard deviation, median, minimum, and maximum) and will be analyzed using an analysis of variance (ANOVA) model or 2-sample t-test for between-group comparisons and paired t-test for within-group analyses. Categorical variables will be summarized by number of patients, frequency count, and percent, and will be analyzed using Pearson's chi-square or Fisher's exact test (if the expected cell count is less than 5 in 25% or more of the cells). Ordinal variables will be analyzed using the Cochran-Mantel-Haenszel (CMH) test or the Wilcoxon rank-sum test for between-treatment comparisons and the signed-rank test for within-treatment comparisons.

A 2-sided test with a p-value ≤ 0.05 will be considered statistically significant unless otherwise stated.

SAT and Prohibited Treatments Impacting Efficacy Assessment

Usage of SAT or prohibited treatments described below will be considered to impact the efficacy assessments for the visit immediately following the use of SAT or prohibited treatments. The subsequent visits will not be impacted, unless the SAT or prohibited treatments are used again prior to any subsequent visits within the timeframe specified below. The efficacy data that are determined to be impacted by the usage of SAT or prohibited treatment will be considered as missing for the continuous variables with the missing data imputation method described below to be implemented. For the analysis of complete response in ocular symptoms, patients will be analyzed as nonresponders for the visits impacted by SAT or prohibited treatments.

- artificial tears (including SAT): use within 24 hours before each scheduled visit (vehicle run-in visit to month 12 visit)
- lid hygiene: use at least 8 days out of the 30-day window preceding each scheduled visit or any use within 14 days before each office visit
- any use during the study after the randomization visit of oral or topical macrolides, tetracyclines, tetracycline derivative drugs

Missing Data Imputation

ITT analyses of the efficacy variables described below will use the following rules to impute the missing data:

- If the data is missing because the patient discontinued the study due to lack of efficacy or use of SAT or other prohibited treatments that impacts the efficacy assessments,

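### Local worsening of burning, blur, discomfort or staining can be misattributed to disease and go unrecorded as an adverse event, and no by-arm table of observed worsening is visible to catch it

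*Combined protocol and SAP*

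**What the plan says.** **Adverse event rule.** Section 9.1.1 defines an adverse event broadly, whether or not it is related to the product. It then makes an exception: new or worsening anticipated signs or symptoms "collected as clinical efficacy variables and assessed as unequivocally associated with the disease progression and /or lack of efficacy, should NOT be reported" in that category. The exception has its own limit, "unless the disease progression is greater than anticipated in the natural course of the disease". Investigators open each visit with a non-directed question, followed by directed questioning and examination as appropriate.

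**Which variables are covered.** Overall discomfort is the primary efficacy measure (6.1.1). Blurred vision, corneal staining and burning are secondary efficacy measures (6.1.2). None of the four is in the safety list (6.3), which does include best-corrected visual acuity (BCVA), biomicroscopy, ophthalmoscopy and intraocular pressure.

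**How they are analysed (7.2.2, 7.3.2).**
- Burning: "Proportion of patients with complete ocular burning response defined as a burning score of 0 will be analyzed as a secondary efficacy variable".
- Blur: "Proportion of patients with complete blurred vision response defined as a blurred vision score of 0 will be analyzed as a secondary efficacy variable".
- Staining: "A responder is defined as a patient with a corneal sodium fluorescein staining score of 0 based on the Oxford scheme".
- Discomfort: complete response (primary), three improvement thresholds, and a change from baseline analysed by ANCOVA.
- The amendment summary (12.3) says that Section 7.2.3 now includes change from baseline in staining and symptom scores, as exploratory analyses.

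**Rescue rule (7.3).** Data affected by artificial tears within 24 hours before a visit, or by listed prohibited treatments, "will be considered as missing for the continuous variables with the missing data imputation method described below to be implemented". That method is last observation carried forward (LOCF).

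**Safety analysis (7.3.4).** The visible text describes treatment-emergent adverse event summaries and leaves detailed methods for safety variables to the analysis plan.

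**The concern.** The same four scores serve as the disease measure and as the likely signal of local intolerance. During the masked phase an investigator must judge which of the two a rise in burning or staining represents. The visible text gives no criterion for that judgement and does not say how much worsening is anticipated. A wrong call in the direction of disease removes the event from the adverse event tables, and the visible efficacy analyses are not built to show it either.

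An acceptable safety profile is one of the two clinical hypotheses (2.2). An excess of local worsening on active drug could be present in the collected scores but under-counted in the reported safety comparison.

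**Working it through.** **1. Is there another visible route by which individual worsening would be seen by arm?**

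| Route | What it shows | What it misses |
|---|---|---|
| Adverse event tables (7.3.4) | Events the investigator reports | Worsening wrongly judged unequivocally due to disease |
| Score-0 response for burning, blur, staining (7.2.2) | Patients reaching 0 at month 6 | Worsening: with entry scores of 1 to 3 (4.3), going from 1 to 4 counts the same as staying at 1 |
| Improvement thresholds for discomfort (7.2.2) | Gains of at least 1 grade, 2 grades or 50% | Any rise |
| Change from baseline (7.2.2; 7.2.3 per 12.3) | Mean shift in each arm | A worsening minority offset by improvers; observed scores replaced by LOCF under the rescue rule |
| Biomicroscopy and BCVA (6.3) | Examination findings and measured acuity | Patient-reported burning and blur |

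Two further limits apply. Efficacy analyses use the study eye only, although both eyes are treated (7.2), so staining in the fellow eye is outside them. The secondary variables are evaluated at month 6, so worsening at earlier visits is outside them too.

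**2. The plan's own sample size, as a check on the formula.** Inputs from 7.6: 20.0% and 9.8%, 237 per group, two-sided 5%, pooled z-test with continuity correction, 10% attrition.

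- Mean proportion = (0.200 + 0.098)/2 = 0.149.
- SE0 = √(2 × 0.149 × 0.851/237) = 0.03271.
- SE1 = √((0.200 × 0.800 + 0.098 × 0.902)/237) = 0.03237.
- z = (0.102 − 1/237 − 1.96 × 0.03271)/0.03237 = 1.040, so power is 85.1%, against 85% stated.
- 474/0.90 = 526.7, which rounds up to 527 as stated, or about 263 per arm.

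**3. Illustration of size.** The documents give no rate of worsening, so every rate here is an assumption. The test is the same without continuity correction: power = Φ((p1 − p2 − 1.96 × SE0)/SE1).

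For 12% against 5% at 263 per arm: mean = 0.085, SE0 = √(2 × 0.085 × 0.915/263) = 0.02432, SE1 = √((0.12 × 0.88 + 0.05 × 0.95)/263) = 0.02413, and z = (0.07 − 0.04767)/0.02413 = 0.926. Power is 82.3%. Extra patients = 263 × 0.07 = 18.

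If only half of these patients have an adverse event recorded in each arm, the rates become 6% and 2.5%. Then SE0 = 0.01759, SE1 = 0.01753, and power is 51%.

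| Assumed worsening, active v vehicle | Extra patients (263 per arm) | Power from observed scores, 263 (237) per arm | Power if half are recorded as adverse events, 263 per arm |
|---|---|---|---|
| 10% v 5% | 13 | 58.6% (54.3%) | 33% |
| 12% v 5% | 18 | 82.3% (78.2%) | 51% |
| 15% v 5% | 26 | 97.1% (95.5%) | 75% |

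The third column describes what the proposed table could detect. The fourth shows what would follow from an assumed 50% recording rate. Neither estimates how many events Section 9.1.1 would in fact keep out.

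**The case against.** - **The exception is narrow.** It requires the link to disease or lack of efficacy to be unequivocal, and it lapses when progression exceeds what is anticipated. An investigator who cannot tell irritation from disease should report the event. This stands. A reader might infer that all worsening of efficacy variables is barred from adverse event reporting, and the text does not say that. What remains is misattribution, because both limits rest on individual judgement.
- **Not every efficacy analysis is score 0.** This also stands. Discomfort has a change score in 7.2.2, and the amendment summary names exploratory change scores for staining and symptoms. The score-0 limitation belongs to the secondary analyses of burning, blur and staining.
- **Other safety measures exist.** Biomicroscopy and visual acuity are listed at every visit from standardization to month 12. They help with surface findings and visual loss, but they do not record patient-reported burning or blur.
- **Text is unavailable.** The body of 7.2.3 and the analysis plan cannot be seen, so one can say only that no worsening table is visible. The deferral in 7.3.4, however, concerns safety variables, and these four scores are not classed as such.
- **The rescue argument is uncertain.** Tears used shortly before a visit might have lowered the score, so the discarded value need not be the worse one. Fair. Even so, the observed score is replaced by an earlier one in patients whose tear use the protocol describes as rescue for intolerable symptoms.
- **Responder rates are not wholly blind.** A patient who would have reached 0 but for irritation lowers the active arm's rate. True, but that shows up as weaker efficacy and is not identified as harm.
- **No signal of irritation.** Section 1 reports all concentrations as safe and well tolerated. That lowers the prior concern but does not replace a by-arm comparison in this trial.

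**Conclusion.** The point holds as a risk of misattribution. Four variables that are plausible local effects of a drop fall within a conditional exception to adverse event reporting. The other visible routes show individual worsening poorly, and no by-arm worsening table is visible. Its size cannot be fixed from the documents: under assumed excesses of 5 to 10 percentage points over a 5% vehicle rate, 13 to 26 extra patients would be affected.

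Three stronger conclusions are not supported: that Section 9.1.1 excludes this worsening outright, that the plan definitely contains no such analysis, and that the drop causes irritation. The power figures are illustrative and do not measure suppressed events. This is a worthwhile, inexpensive improvement to the safety analysis. It does not affect the primary analysis.

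**What to change.** Add to Section 7.3.4, for the safety population in the masked phase and by arm, the number and percent of patients whose score rises from day 1 by at least 1 grade and by at least 2 grades in ocular burning, blurred vision, overall discomfort and corneal staining (staining for each eye).

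- Report it at each masked-phase visit where the score is collected, and as any such visit combined. Staining is visibly scheduled at months 1, 3 and 6 (8.3.5 to 8.3.7). Symptom collection at months 1 and 3 cannot be confirmed from the public text.
- Use observed scores regardless of rescue or prohibited treatment, without LOCF.
- Give the between-arm difference with a 95% confidence interval.

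If the analysis plan already contains this table, a cross-reference in 7.3.4 is enough.

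The cost is one or two extra tables from scores the trial already collects. Some ordinary disease fluctuation will be counted as worsening, but in both arms, and the vehicle arm shows the background rate. No treatment rule, visit or efficacy analysis changes.

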9.1.2 Serious Adverse Event

A serious adverse event is any adverse event occurring at any dose that results in any of the following outcomes: death, a life-threatening adverse event, inpatient hospitalization or prolongation of existing hospitalization, a persistent or significant disability/incapacity, or a congenital anomaly/birth defect. Important medical events that may not result in death, be life-threatening, or require hospitalization may be considered a serious adverse event when, based upon appropriate medical judgment, they may jeopardize the patient or subject and may require medical or surgical intervention to prevent one of the outcomes listed in this definition. (See [Section 9.3](#) for procedures for reporting a serious adverse event.)

Allergan considers all cancer adverse events as serious adverse events. In addition, Allergan considers any abortion (spontaneous or nonspontaneous) as a serious adverse event.

Pre-planned surgeries or procedures for pre-existing, known medical conditions for which a patient requires hospitalization is not reportable as a serious adverse event.

Any pre-planned surgery or procedure should be clearly documented in the site source documents by the medically qualified investigator at the time of the patient's entry into the

study. If it has not been documented at the time of the patient's entry into the study, then it should be documented as a serious adverse event and reported to Allergan.

9.1.3 Severity

A clinical determination will be made of the intensity of an adverse event. The severity assessment for a clinical adverse event must be completed using the following definitions as guidelines:

Mild	Awareness of sign or symptom, but easily tolerated.
Moderate	Discomfort enough to cause interference with usual activity.
Severe	Incapacitating with inability to work or do usual activity.

9.1.4 Relationship to Study Drug or Study Procedure

A determination will be made of the relationship (if any) between an adverse event and the study drug or study procedure, as applicable. A causal relationship is present if a determination is made that there is a reasonable possibility that the adverse event may have been caused by the drug or study procedure.

9.2 Procedures for Reporting Adverse Events

Any adverse event must be recorded on the appropriate case report form.

All adverse events that are drug-related and unexpected (not listed as treatment-related in the current Investigator's Brochure) must be reported to the governing Institutional Review Board/Independent Ethics Committee (IRB/IEC) as required by the IRB/IEC, local regulations, and the governing health authorities. Any adverse event that is marked 'ongoing' at the exit visit must be followed-up as appropriate.

9.3 Procedures for Reporting a Serious Adverse Event

Any serious adverse event occurring during the study period (beginning with informed consent) and for at least 28 days after the last dose of study drug must be immediately reported but no later than 24 hours after learning of a serious adverse event. Serious adverse events must be reported to Allergan (or Agent of Allergan eg, CRO as listed on the Allergan Study Contacts Page and recorded on the serious adverse event form. All patients with a serious adverse event must be followed up and the outcomes reported. The investigator must

supply the sponsor and the IRB/IEC with any additional requested information (eg, autopsy reports and discharge summaries).

In the event of a serious adverse event, the investigator must:

1. Notify Allergan immediately by fax or email using the serious adverse event form (contact details can be found on page 1 of the serious adverse event form); phone numbers and relevant Allergan personnel contacts are also on the front page of protocol and Study Contacts Page.
2. Obtain and maintain in his/her files all pertinent medical records, information, and medical judgments from colleagues who assisted in the treatment and follow-up of the patient.
3. Provide Allergan with a complete, written description of the adverse event(s) on the serious adverse event form describing the event chronologically, including any treatment given (eg, medications administered, procedures performed) for the adverse event(s). Summarize relevant clinical information about the event: signs, symptoms, diagnosis, clinical course and relevant clinical laboratory tests, etc. Include any additional or alternative explanation(s) for the causality which includes a statement as to whether the event was or was not related to the use of the investigational drug.
4. Promptly inform the governing IRB/IEC of the serious adverse event as required by the IRB/IEC, local regulations, and the governing health authorities.

9.4 Procedures for Unmasking of Study Medication

When necessary for the safety and proper treatment of the patient, the investigator can unmask the patient's treatment assignment to determine which treatment has been assigned and institute appropriate follow-up care. When possible, the sponsor (Allergan Medical Safety Physician) should be notified prior to unmasking study medication. The investigator should inform the sponsor (Allergan Medical Safety Physician) of the unmasking if there is no notification prior to the unmasking.

The treatment assignment for the patient can be determined by designated site personnel calling into the IVRS or IWRS system via password protected access. The reason for breaking the code must be recorded in the patient's source documents.

10. Administrative Items

This protocol is to be conducted in accordance with the applicable Good Clinical Practice (GCP) regulations and guidelines, eg, the International Conference on Harmonisation (ICH) Guideline on GCP.

10.1 Protection of Human Patients

10.1.1 Compliance with Informed Consent Regulations (US 21 CFR Part 50) and Relevant Country Regulations

Written informed consent is to be obtained from each patient prior to any study-related activities or procedures in the study, and/or from the patient's legally authorized representative. If the patient is under the legal age of consent, the consent form must be signed by the legally authorized representative in accordance with the relevant country and local regulatory requirements.

10.1.2 Compliance With IRB or IEC Regulations

This study is to be conducted in accordance with IRB regulations (US 21 CFR Part 56.103) or applicable IEC regulations. The investigator must obtain approval from a properly constituted IRB/IEC prior to initiating the study and re-approval or review at least annually. Allergan is to be notified immediately if the responsible IRB/IEC has been disqualified or if proceedings leading to disqualification have begun. Copies of all IRB/IEC correspondence with the investigator should be provided to Allergan.

